2.3 Historical Information

Historical information elicited will include the following: date of birth, sex, race, ethnicity, cycloplegic refraction, cycloplegic autorefraction (performed within 2 months or at enrollment), prior treatment for IXT, spectacle correction, and use of ADHD and anti-seizure medications.

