5.3.1.2 Near Control

At both the 12-month and 18-month time points, near control will be evaluated similarly to the distance control primary analysis (*section 5.1.1*) and secondary analysis (*section 5.1.2*).

1763 5.3.1.3 Angle Magnitude

- 1764 At both the 12-month and 18-month time points, a two-sided comparison of magnitude of the
- deviation by Prism Alternate Cover Test (PACT) will be compared between treatment groups
- using an ANCOVA model, which adjusts for baseline PACT. The treatment group difference
- and a 95% confidence interval will be calculated. The analysis will be completed separately at
- distance and at near.

1769

1770 **5.3.1.4 Stereoacuity**

- 1771 At both the 12-month and 18-month time points, a two-sided comparison of near stereoacuity by
- 1772 Preschool Randot Test will be compared between treatment groups using an ANCOVA model
- which adjusts for baseline stereoacuity. The treatment group difference and a 95% confidence
- interval will be calculated.

1775

1776 5.3.1.5 Axial Length Measurement at 18 Months

- Mean 18-month axial length measurement will be compared between treatment groups using an
- 1778 ANOVA model. The treatment group difference and a 95% confidence interval will be
- calculated. Adjustment for baseline is not possible given that these measurements were added
- late in the study (with Protocol Amendment II), long after recruitment had ended.

1781

1782 5.3.1.6 Additional Ocular Biometric Parameters at 18 Months

- Mean 18-months flat corneal radius, anterior chamber depth, and lens thickness will each be
- 1784 compared between treatment groups using an ANOVA model. The treatment group difference
- and a 95% confidence interval will be calculated. Adjustment for baseline is not possible given
- that these measurements were added late in the study (with Protocol Amendment II), long after
- 1787 recruitment had ended.

17881789

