35 on SE in the least hyperopic eye as follows: 1) full correction for SE myopia, 2)
36 sphere power that resulted in a plano SE lens (with symmetrical reduction in the
37 most hyperopic eye, if needed).

38
39 Note: any mention of refractive error from this point on will refer to refractive error in the
40 most myopic eye at baseline; this is because treatment was prescribed based on this eye
41 and eligibility criteria, so this is the eye that will be used for any analyses involving
42 refractive error.

43
44 **2. Objective I: Effect of Overminus Lenses on Distance Control**

45
46 **2.1 Primary Analysis – Efficacy of Overminus Treatment (12 Months, On-
47 Treatment)**

48 The primary analysis will be a two-sided comparison of mean 12-month control of the
49 distance exodeviation (mean of 3 measurements) between the treatment groups using an
50 analysis of covariance (ANCOVA) model which adjusts for the following baseline
51 factors to account for potential residual confounding: distance control, distance PACT,
52 age, and refractive error (in the most myopic eye at baseline). The ANCOVA model will
53 test the hypothesis that the treatment effect is different from zero (superiority hypothesis)
54 using a type I error rate of 5%. The treatment group difference (overminus – non-
55 overminus) and corresponding 95% confidence interval and p-value will be calculated.
56 While use of ADHD medication was specified in the protocol as a baseline adjustment
57 factor, this information was not collected at baseline due to an oversight. Therefore, this
58 will not be one of the adjustment factors in the model.

59
60 **2.1.1. Principles to be Followed in Primary Analysis**

61 Model assumptions for the ANCOVA will be assessed, including linearity of the
62 adjustment covariates (baseline distance control, distance PACT, age, and refractive
63 error), normal distribution and equal variance across the treatment groups. The linearity
64 assumption of the baseline covariates will be evaluated using descriptive scatterplots and
65 by categorizing each of the baseline factors in the model to check for approximate
66 linearity of the coefficients across ordered categories. A baseline covariate will be
67 included as a continuous variable in the model if the assumptions for linearity are met for
68 that covariate; otherwise, the baseline covariate will be categorized.

69
70
71
72
73
74
75
76
77
78
79
80
81
82
83
84
85
86
87
88
89
90
91
92
93
94
95
96
97
98
99
100
101

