191 no statistical testing. The analyses involving 12-month data will be conducted using
192 available 12-month outcome data in accordance with the specifications laid out in this
193 SAP.
194

195 **2.1.9. Multiple Imputation of Missing Values**

196 The multiple imputation will be performed for missing data using Monte Carlo Markov
197 Chain (MCMC) modeling, which includes the mean distance control scores at all follow-
198 up visits prior to and including the 12-month visit, and the following baseline factors:
199 distance PACT, age, and refractive error. The mean distance control score will be used in
200 the MCMC model when multiple baseline measurements are available. The multiple
201 imputation will be performed separately by treatment group to account for potential
202 interaction between the treatment groups and the follow-up distance control scores. The
203 number of imputations will be set to 100. For the participants who started IXT treatment
204 other than overminus or non-overminus spectacles, only data from the visits prior to
205 starting such treatment will be used in the MCMC model. Missing baseline data are not
206 expected for distance PACT, age, and refractive error; however, if such missing data

207 occurs, it will be imputed in the MCMC model so that participants with such missing
208 baseline data are included in the analysis.

209

210 If the study is not terminated early based on partial or complete 12-month data (as
211 specified in Section 2.3), the missing mean distance control scores at all follow-up visits
212 (including 15-month and 18-month visits) will be imputed again using an MCMC model
213 that includes mean distance control scores at all follow-up visits prior to and including
214 the 18-month visit, following the same principles specified above for the imputation of
215 primary outcome at 12 months. Both the primary analysis for the 12-month outcome
216 specified in Section 2 (including sensitivity analyses) and the secondary analysis for the
217 18-month outcome outlined in this SAP will be conducted using this newly imputed
218 dataset and the results will be used in the final manuscript.

219

220

221 **2.2 Secondary Analysis: Efficacy of Overminus After Treatment Discontinuation** 222 **(18 Months, Off-Treatment)**

223

224 The analyses specified in the secondary analysis will be performed on the full cohort
225 which includes participants who were and were not prescribed full treatment between 0 to

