419 whether the incorrectly-assigned value matched the assignment that would have been
420 chosen if the correct record from the randomization schedule was used. The imputed
421 dataset specified in Section 2.1.9 will be used. The results will be compared to the
422 original analyses to assess if bias was introduced by including these 28 participants who
423 were included in in the primary analyses despite being incorrectly randomized.

424

425 **4.1.4 Near Control**

426 At the 12 and 18-month time points, near control will be evaluated similarly to the
427 distance control primary analysis (Section 2).

428

429 **4.1.5 Angle Magnitude by PACT**

430 At the 12- and 18-month time points, a two-sided treatment group comparison of
431 magnitude of the deviation by Prism Alternate Cover Test (PACT) will be performed
432 using an ANCOVA model which adjusts for baseline PACT. The treatment group
433 difference, 95% confidence interval and p value will be calculated. The analysis will be
434 completed separately for distance PACT and at near PACT.

435

436 **4.1.6 Stereoacuity**

437 At the 12 and 18-month time points, a two-sided treatment group comparison of near
438 stereoacuity (measured with the Preschool Randot Test) will be performed using an
439 ANCOVA model which adjusts for baseline stereoacuity. The treatment group difference,
440 95% confidence interval, and p value will be calculated.

441

442 **4.1.7 Axial Length Measurement**

443 At the 18-month time point, mean axial length measurement will be compared between
444 treatment groups using an ANOVA model. The treatment group difference and a 95%
445 confidence interval will be calculated. Adjustment for baseline is not possible given that
446 these measurements were added late in the study (with Protocol Amendment II) and
447 therefore not collected at baseline.

448

449 **4.1.8 Additional Ocular Biometric Parameters**

450 At the 18-month time point, mean flat corneal radius, anterior chamber depth, and lens
451 thickness will each be compared (if available) between treatment groups using an
452 ANOVA model. The treatment group difference and a 95% confidence interval will be
453 calculated. Adjustment for baseline is not possible given that these measurements were
454 added late in the study (with Protocol Amendment II) and therefore not collected at
455 baseline.

456

457 **4.1.9 Refractive Error**

458 At the 12- and 18-month time points, a two-sided treatment group comparison of

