At the 24-month and 36-month time points, mean axial length measurement, flat corneal radius, anterior chamber depth, and lens thickness (if available) will each be compared between treatment groups using an ANOVA model. Adjustment for baseline is not possible given that these measurements were added late in the study (with Protocol Amendment II) and therefore not collected at baseline. Treatment group differences, 95% confidence intervals, and p-values will be calculated. The type I error rate in this secondary analysis will be controlled using false discovery rate (FDR) to control the FDR at 5% and to adjust the p-values for multiplicity.

Longer axial length is expected to be related to more myopic progression. The other biometric measures may or may not be related to myopic progression. To assess this, Spearman correlation coefficients will be calculated for the relationship between the biometric measures (mean axial length measurement, flat corneal radius, anterior chamber depth, and lens thickness) and refractive error at the 24-month and 36-month time points. Correlation coefficients with an absolute value of 0.60 or higher will be considered strong correlations.

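### Axial length and other biometry are compared by unadjusted ANOVA, although baseline refraction and age are available as covariates; the likely loss is precision, of unknown size

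*SAP*

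**What the plan says.** - **Model.** Protocol 5.3.1.5: "Mean 18-month axial length measurement will be compared between treatment groups using an" ANOVA model. Protocol 5.3.1.6 treats corneal radius, chamber depth and lens thickness alike. SAP 4.1.7 and 4.1.8 repeat this at 18 months, and SAP 5.3 applies it at 24 and 36 months: the measures "will each be compared between treatment groups using an ANOVA model. Adjustment for baseline is not possible given that these measurements were added late".
- **Reason given.** In each place the reason is that biometry came in with Amendment II and has no baseline value: "Adjustment for baseline is not possible given that" it was not collected then.
- **Covariates held.** Protocol 2.3: "Historical information elicited will include the following: date of birth, sex, race, ethnicity, cycloplegic refraction". SAP 2.1.9 does not expect age or refractive error to be missing at baseline.
- **Covariates used elsewhere.** The primary model in SAP 2.1 includes "age, and refractive error (in the most myopic eye at baseline"). SAP 4.1.9 adjusts 12- and 18-month refractive error for baseline refraction and age, and labels age post hoc. SAP 1 fixes the most myopic eye at baseline for refraction: "so this is the eye that will be used for any analyses involving" refractive error.
- **Nearest substitute.** SAP 5.5.4 tabulates 24- and 36-month biometry by baseline refraction subgroup. It gives no adjusted group difference and does not cover 18 months.

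**The concern.** Amendment II (Protocol Change #4) added biometry because the overminus group showed more myopic progression and the study wanted to know whether axial length differed too. With no baseline biometry, all the natural variation between children stays in the error term. Correlated baseline variables are then the only way to reduce it, and two candidates are in the database with almost no missing values. The stated reason for leaving them out covers only one kind of adjustment.

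What is at stake is the width of the confidence intervals, and how far a chance difference between groups in baseline refraction or age could mask or imitate a difference in biometry. Biometry is measured only where a site has a device. At 18 months it is also limited to visits after the amendment, so the samples may be small.

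**Working it through.** **The plan's own figures.** The documents state no sample size, SD, power or correlation for biometry, so there is no figure to reproduce directly. Protocol 5.7.1 does recognise the principle: it considers shrinking the distance-control sample by (1 − r²). Its base figure reproduces: a difference of 0.65, SD 1.8, two-sided 0.05 and 90% power give 163 per group by t-test, 326 in total. At r = 0.25, 326 × (1 − 0.0625) ≈ 306, a saving of about 20, in line with the protocol's remark.

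**Inputs for biometry.**
- R² of the outcome on baseline refraction and age: not in the documents. Assumed 0 to 0.50.
- N with biometry: not in the documents. Protocol 5.3.2.2 and SAP 4.2.2 expect 355 visits at 18 months, with about 283 children completing full weaning. This leaves 355 − 283 = 72, which agrees with the partial and no-weaning counts (35 + 37 = 54 + 18 = 72). The percentage printed beside 35 to 54 (20% to 25%) does not match those counts (35/355 = 9.9%, 54/355 = 15.2%), so only counts are used.
- The values 72 and 355 serve to show a range. An unknown share of the 283 would also be measured after the amendment, while missed visits and sites without a device reduce the number. So 72 is neither a floor nor an estimate, and 355 is an upper limit for 18 months. No count is given for 24 or 36 months.

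**Formulas** (two equal groups, half-width of the 95% CI in SD units):
- ANOVA: t(0.975, N − 2) × √(4/N)
- ANCOVA with two covariates: t(0.975, N − 4) × √[(1 − R²) × (4/N) × (N − 3)/(N − 5)]

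The last factor is the expected cost of estimating two covariates.

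**Example, N = 72, R² = 0.25.** ANOVA: 1.994 × √(4/72) = 0.470. ANCOVA: 1.995 × √(0.75 × 0.05556 × 69/67) = 0.413. The interval is 12% narrower.

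| N | ANOVA | R² = 0 | R² = 0.10 | R² = 0.25 | R² = 0.50 |
|---|---|---|---|---|---|
| 72 | 0.470 | 0.477 (+1.5%) | 0.453 (−3.7%) | 0.413 (−12.1%) | 0.338 (−28.2%) |
| 150 | 0.323 | 0.325 (+0.7%) | 0.308 (−4.5%) | 0.281 (−12.8%) | 0.230 (−28.8%) |
| 355 | 0.209 | 0.209 (+0.3%) | 0.199 (−4.9%) | 0.181 (−13.2%) | 0.148 (−29.1%) |

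The break-even R² is 0.03 at N = 72 and 0.006 at N = 355. A simulation at N = 72 (4,000 trials) gave width changes of +1.5, −3.7, −12.1 and −28.2%, matching the formula. A separate simulation at N = 200 with random allocation found no bias in either model (mean error at most 0.002 SD).

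**Timing.** Amendment II says that in November 2019 all children had at least 9 months of treatment and that the last 12-month visits were planned by December 2019. The last randomizations therefore fell at about December 2018 to February 2019. Their nominal 36-month dates are about December 2021 to February 2022, after SAP v2.2 (25 February 2021). The protocol allows a further 3 months, and SAP 5.2.1 accepts visits up to 1440 days (48 months). So 36-month collection was still open at v2.2, while the 18-month data and most 24-month data were probably in hand.

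**The case against.** The strongest reply is that nothing here is wrong. A two-group ANOVA is unbiased under randomization and keeps its type I error. The SAP usually adjusts a secondary continuous outcome for its own baseline value (angle magnitude, stereoacuity), and read that way its sentence about baseline is accurate. The model was fixed in the protocol when biometry was introduced, and biometry is secondary. All of this stands, and it makes the point an efficiency improvement rather than an error. It does not make the ANOVA efficient.

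Two stronger readings are tempting and not supported:

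- **That the loss falls chiefly on axial length.** A reader might infer this from SAP 5.3, which expects longer axial length to go with more myopic progression and adds: "The other biometric measures may or may not be related to myopic progression". That passage is about progression, and its planned correlations use refraction at 24 and 36 months. The precision gain depends on how well baseline refraction and age predict later biometry, which no section addresses.
- **That the unadjusted comparison is biased.** It could be if the chance of being measured depended on baseline refraction differently by group. Nothing in the documents shows that it did.

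It is also fair to say that the 18-month sample may be the most restricted, yet that is where an adjusted model could now only be post hoc. Finally, the SAP text between 4.3.1 and 5.2.1 is not in the copy available, so general covariate wording there cannot be excluded. The explicit ANOVA wording in 4.1.7, 4.1.8 and 5.3 would still govern these measures.

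**Conclusion.** The point holds as a modest, inexpensive improvement. The stated reason excludes adjustment for baseline biometry only. Baseline spherical equivalent and age are collected, expected to be complete, and used as covariates in other models of the same SAP.

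The likely loss is precision and protection against chance imbalance. It ranges from nothing to more than a quarter of the interval width across the assumed R² of 0 to 0.50, against a worst-case cost of about 1.5% if the covariates are useless. These figures rest on assumed R² and N, equal groups, and measurement that does not depend on baseline refraction differently by group. A useful gain for axial length is plausible; for the other three measures it may be nil. The specified ANOVA remains a valid analysis.

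**What to change.** In SAP 4.1.7, 4.1.8 and 5.3:

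1. Add an ANCOVA for each biometric measure, adjusting for baseline cycloplegic spherical equivalent in the most myopic eye at baseline and for baseline age. Take the biometry from that same eye and say so, since these sections do not name the eye. Do not use follow-up refraction as a covariate, because treatment can affect it.
2. Report it beside the specified ANOVA. Make it the main analysis where the data have not been examined, chiefly at 36 months. Elsewhere keep the ANOVA as main and label the ANCOVA post hoc, as SAP 4.1.9 does for age.
3. State which model's p-values enter the false-discovery-rate families in SAP 4 and 5.3, so that the extra model does not enlarge them.
4. Reword the rationale to say that adjustment for the baseline value of the same measure is not possible.

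The cost is SAP wording and one extra model per measure, with covariates already held and no new data. The drawback is a departure from the ANOVA set when biometry was introduced, which is why the label should depend on whether the data had been seen.

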5.4. Exploratory Analyses

The analyses described in the sections below will be exploratory because treatment for IXT was at investigator discretion after 18 months. For each outcome, a difference between treatment groups and 95% CI will be estimated, but p-values will not be calculated. If the outcome is continuous, the difference and 95% CI will be calculated using an ANCOVA model adjusted for the baseline value of the measure, as was done for the continuous outcomes in Section 4. If the outcome is categorical (i.e., a proportion), a two-sided Barnard’s exact test will be used as was done in Section 4.1.1.

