The parent/guardian of each subject will be compensated \$50 for completion of each of the 24-month and 36-month visits, up to a total of \$100. If there are extenuating circumstances, and the subject is unable to complete the annual study visits without additional funds due to travel costs, additional funds may be provided.

The study will pay for visits specific to the research study, but will not pay for usual care visits that would occur whether or not the subject was in the study. The cost of usual care visits will be the responsibility of the subject or his/her insurance company.

The study will pay for a pair of spectacles (lenses and frames) at the first extension study visit (24 months or 36 months). Spectacle changes / new spectacles prescribed at other times will not be paid for by the study.

Treatment after 18-months is at investigator discretion and is not part of this protocol. Any costs associated with treatment will not be paid for by the study.

Risks

The procedures in this study are part of daily eye care practice in the United States and pose no known risks.

Subject Contact During Follow Up

Between annual visits, subjects may be called periodically by the Jaeb Center to promote retention.

Re-consenting of Subjects

An addendum to the original informed consent form (and addendum to the assent form, if required) for the extension study will be signed by parents who elect to continue their child's study participation. Re-consenting will occur at the next 12, 15, or 18-month randomized trial visit but could occur at other times either before or after participation in the 18-month trial has ended. A subject (and respective parent) may withdraw from the study at any time.

294295 Statistical Analyses

The following analyses will be completed separately at the 24-month and 36-month visits to evaluate the effect of the overminus treatment approach followed by usual clinical care versus the non-overminus treatment approach followed by usual clinical care:

- Spherical equivalent refractive error will be compared between treatment groups using an ANCOVA model that adjusts for baseline spherical equivalent refractive error. The treatment group difference and a 95% confidence interval will be calculated.

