- Mean distance control (average of 3 measurements) will be compared between treatment groups using an analysis of covariance (ANCOVA) model, which adjusts for baseline distance control, distance PACT, age, refractive error, and use of ADHD medication, to address potential residual confounding.
- The proportion of subjects with no spontaneous tropia will be compared between treatment groups as in section 5.1.2.1.
- Axial length, flat corneal radius, anterior chamber depth, and lens thickness (if available) will be compared between treatment groups as in section 5.3.2.3 and
- Secondary outcomes of near control, angle magnitude, and near stereoacuity will also be compared between treatment groups as in section 5.3.1.
- Treatments used since the last visit will be tabulated by treatment group.

	PROTOCOL AMENDMENT I (11-8-16)
]	This amendment provides for the following protocol changes:
]	Protocol Change #1
r	Original Protocol At the time of enrollment and each follow-up visit at 6, 12, 15, and 18 months, parents are asked to respond to a survey of symptoms potentially associated with spectacle treatment (headaches, eye strain, and other problems with spectacle wear) based on their observations of their child in the past weeks.
(Changed Protocol
1	 To add a 7-question survey of intermittent exotropia symptoms to be administered to the child. To add a health-related quality of life questionnaire to evaluate whether either treatment impacts the effect of intermittent exotropia on quality of life.
	• Children ages 5 and older at the time of enrollment will complete an 11-item questionnaire to assess how their eye condition affects their quality of life. Children years of age and younger at the time of enrollment will not complete the child questionnaire.
	 A 16-item parental questionnaire will assess how the child's eye condition affects the quality of life of the parent (for all subjects).
3	3. The surveys and questionnaires will be completed at the time of enrollment; and at 6-month, 12-month, and 18-month follow-up visits.

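### For distance control at 24 and 36 months, SAP 5.4 adjusts only for the baseline value, while the protocol also names distance PACT, age and refractive error; no reason is given and the SAP's reference to Section 4 is partly wrong.

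*SAP*

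**What the plan says.** **Protocol, Amendment II, Change #6 (extension), Statistical Analyses.** The list opens with "The following analyses will be completed separately at the 24-month and 36-month visits to evaluate" the two treatment strategies. For distance control it states: "Mean distance control (average of 3 measurements) will be compared between treatment groups using an analysis of covariance (ANCOVA) model". On the choice of covariates, that analysis is described as one "which adjusts for baseline distance control, distance PACT, age, refractive error, and use of ADHD medication, to address potential residual confounding". For near control it points elsewhere: "Secondary outcomes of near control, angle magnitude, and near stereoacuity will also be compared between treatment groups as in section 5.3.1". Protocol 5.3.1.2 in turn models near control on the primary distance-control analysis of 5.1.1.

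**SAP 5.4.** These analyses are labelled exploratory because treatment is left to the investigator once 18 months have passed. A group difference and 95% confidence interval are estimated, without p-values. Continuous outcomes are handled "using an ANCOVA model adjusted for the baseline value of the measure, as was done for the continuous outcomes in Section 4". SAP 5.4.2 (distance control) and 5.4.3 (near control) name no further covariates.

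**SAP 2.1.** The 12-month primary model, repeated at 18 months under 2.2.1, adjusts for baseline "factors to account for potential residual confounding: distance control, distance PACT", age and refractive error. ADHD medication is left out, with the explanation that it was not recorded at baseline.

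**SAP 4.1.4.** "At the 12 and 18-month time points, near control will be evaluated similarly to the" primary distance-control analysis of Section 2.

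**The concern.** The protocol fixed a covariate set for this outcome at these two visits, and the SAP uses a smaller one. One of the four covariates dropped (ADHD medication) has a documented reason. The other three (distance PACT, age, refractive error) are baseline measurements that the SAP already uses for the same outcome at 12 and 18 months, so availability cannot be the reason.

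Two things are at stake. The first is an unexplained departure from the stated model, which a reader comparing protocol, SAP and publication will notice. The second is some precision, and some protection against chance imbalance in the covariates left out. There is also a practical matter: a programmer told to adjust near control for its baseline value, and also to do as Section 4 did, receives two instructions that do not agree.

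**Working it through.** **Step 1. Covariates for control outcomes, side by side.**

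| Outcome and visit | Source | Covariates |
|---|---|---|
| Distance control, 12 and 18 months | SAP 2.1, 2.2.1 | baseline distance control, age, distance PACT, refractive error |
| Distance control, 24 and 36 months | Protocol Amendment II | the same four plus ADHD medication |
| Distance control, 24 and 36 months | SAP 5.4, 5.4.2 | baseline distance control only |
| Near control, 24 and 36 months | Protocol Amendment II, via 5.3.1.2 and 5.1.1 | analogous to the distance-control model |
| Near control, 24 and 36 months | SAP 5.4, 5.4.3 | baseline near control only |

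The mismatch is explicit for distance control. For near control it arises only through cross-references.

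**Step 2. Is a reason given?** SAP 2.1 covers ADHD medication only. The revision history records that the extension sections were added in version 2.0. For version 2.2 it lists changes to visit windows, sensitivity analyses, tabulations and correlations. Neither entry mentions covariates for control. Elsewhere the SAP does explain such choices: 3.1 limits adjustment because few deteriorations were expected, and 4.1.9 labels age as a post-hoc addition. The reason given for exploratory status concerns post-randomisation treatment and does not bear on baseline covariates.

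**Step 3. Does the reference to Section 4 hold?**

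| SAP section | Outcome | Baseline value only? |
|---|---|---|
| 4.1.4 | near control | no, follows the Section 2 analysis |
| 4.1.5 | PACT | yes |
| 4.1.6 | stereoacuity | yes |
| 4.1.9 | refractive error | no, also adjusts for age |

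Distance control is not itself a baseline-only ANCOVA anywhere in Section 4. SAP 4.1.2 reports distributions and proportions, and 4.1.3 repeats the Section 2 comparison. The reference is therefore right for two outcomes and wrong for two.

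**Step 4. Size.** No figure in the plan depends on this choice, so the calculation is for scale only. Inputs from Protocol 5.7.1 are SD 1.8 points, baseline-to-outcome correlation 0.25 (observed at 8 weeks in the pilot) and 163 per group. The share of residual variance explained by the three omitted covariates, R², is not in the documents; I assume 0 to 0.10.

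Baseline control alone explains 0.25² = 0.0625 of the variance. The half-width of the 95% interval is 1.96 × 1.8 × √(1 − 0.0625) × √(1 − R²) × √(2/163).

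| Assumed R² | Half-width (points) | Narrowing, 1 − √(1 − R²) | Equivalent extra sample, 1/(1 − R²) − 1 |
|---|---|---|---|
| 0 | 0.378 | 0% | 0% |
| 0.02 | 0.375 | 1.0% | 2.0% |
| 0.05 | 0.369 | 2.5% | 5.3% |
| 0.10 | 0.359 | 5.1% | 11.1% |

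The narrowing does not depend on the SD, the number of children or the 0.25. Fewer children at 24 or 36 months would widen every row by the same factor.

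**The case against.** The strongest reply is that nothing rests on this. The extension's objective is refractive error, the control analyses are exploratory without p-values, and an ANCOVA on the baseline value alone is a valid analysis of a randomised comparison. All of that stands, and it limits the weight of the point.

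A second reply is that the final SAP supersedes the protocol. The clause in Protocol Chapter 5 applies to the synopsis in that chapter. The extension's distance-control model is written in Amendment II, outside it. Supersession would also not repair the reference to Section 4.

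A third is that a reason may sit in the SAP text between 4.3.1 and 5.2.1, which was not available. That cannot be excluded. What can be said is that 5.4 and the revision history give none.

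A reader might also infer more than the documents support:

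- *That a shift in effect between 18 and 24 months could be put down to the change of model, and that a common covariate list would make the visits comparable.* At 12 and 18 months, missing outcomes and outcomes after non-study treatment are multiply imputed. SAP 5.2.1 states no imputation for the extension's primary analysis, and treatment after 18 months is unrestricted. These differences would remain with identical covariates.
- *That attrition was ignored.* SAP 5.2.1 compares baseline characteristics of children with and without follow-up and provides a propensity-weighted sensitivity analysis. It is written for refractive error, but it shows that attrition was considered. The documents do not show that returning children are imbalanced.
- *That near control should carry both baseline near and baseline distance control.* Neither document specifies this. The natural reading of 4.1.4 is the Section 2 model with baseline near control in place of baseline distance control.

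**Conclusion.** The point holds as an unexplained mismatch. For 24- and 36-month distance control, the SAP omits three covariates that the protocol names and that the trial already uses at earlier visits. Its justification by reference to Section 4 is accurate for PACT and stereoacuity only.

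The size is small: a narrowing of about 0% to 5% in the confidence interval, resting on an assumed 0% to 10% of residual variance explained. The reduced model is not shown to be biased, and no confirmatory conclusion depends on it. The reason to act is agreement between protocol and SAP and an unambiguous instruction for near control, with a little precision as a by-product. This is a desirable improvement, not a defect that threatens the results.

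**What to change.** In SAP 5.4:

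- State that 5.4.2 uses an ANCOVA with baseline distance control, age, refractive error and distance PACT. This is the protocol's model without ADHD medication, whose omission SAP 2.1 already explains.
- State that 5.4.3 uses the same model as 4.1.4, with baseline near control replacing baseline distance control.
- Limit the reference to Section 4 to the outcomes it fits (4.1.5 and 4.1.6).

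If the reduced model is preferred, say so, give the reason, and still correct the reference.

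The cost is a few sentences. The covariates are already in the 12- and 18-month models, so no new data are needed, and three extra model terms cost a negligible number of degrees of freedom. If estimates from all four visits are shown together, add a note that imputation and treatment after 18 months also differ.
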